5 SEPT, 2018

Date

EU Qualified Person Responsible for
Pharmacovigilance

PASS INFORMATION

Title	The Benralizumab Pregnancy Exposure Study: A VAMPSS Post-Marketing Surveillance Study
Protocol version identifier	2.0
Date of last version of protocol	23 March 2018
EU PAS register number	Study not registered
Active substance	Benralizumab
Medicinal product	Fasenra TM
Product reference	Benralizumab
Procedure number	EMA/H/C/004433/MEA/003
Marketing authorisation holder(s)	AstraZeneca AB
Joint PASS	No

Research question and objectives	The objectives of the Pregnancy Exposure Study are to monitor planned and unplanned pregnancies exposed to benralizumab and to evaluate the possible teratogenic effect of this medication relative to the primary pregnancy outcome of major structural birth defects and the secondary pregnancy outcomes of preterm delivery, small for gestational age infants, spontaneous abortion, stillbirth, elective termination and small for age postnatal growth to one year of age.
Country (-ies) of study	United States and Canada (North America)
Author(s)	[name], MPH Professor of Pediatrics School of Medicine University of California San Diego [name] Tel: [REDACTED] Email: [REDACTED]

2. LIST OF ABBREVIATIONS

Abbreviation or special term	Explanation
AAAAI	American Academy of Allergy, Asthma and Immunology
AZ	AstraZeneca
CDC	Centers for Disease Control and Prevention
EMA	European Medicines Agency's
FDA	Food and Drug Administration
FPI	First Patient In
GA	Gestational Age
HIPAA	Health Insurance Portability and Accountability Act
IRB	Institutional Review Board
LMP	Last Menstrual Period
MACDP	Metropolitan Atlanta Congenital Defects Program
MAH	Marketing Authorization Holder
MCM	Major Congenital Malformation
NCHS	National Center for Health Statistics
OTIS	Organization of Teratology Information Services
PASS	Post-Authorization Safety Studies
PRAC	Pharmacovigilance Risk Assessment Committee
PTB	Preterm Birth
SAE	Serious Adverse Event
SAP	Statistical Analysis Plan
SOP	Standard Operating Procedures
UCSD	University of California, San Diego
US	United States
VAMPSS	Vaccines and Medications in Pregnancy Surveillance System

4. ABSTRACT

Title: The Benralizumab Pregnancy Exposure Study: A VAMPSS Post-Marketing Surveillance Study

Rationale and background: Asthma in women of child bearing age and pregnant women is common. Although the majority of patients with asthma can be effectively treated with available controller medications, a subset of patients does not adequately respond to current standard therapy. Benralizumab (Fasenra™) is an eosinophil depleting monoclonal antibody (IgG1 kappa) indicated in EU as an add-on maintenance treatment in adult patients with severe eosinophilic asthma inadequately controlled despite high-dose inhaled corticosteroids plus long-acting β -agonists.

Pregnancy exposure data for benralizumab is insufficient to inform regarding drug-associated risks to the fetus or mother. Nonetheless, benralizumab is likely to be utilized by pregnant women when they and their doctors believe that risk/benefit considerations favor its use. Also, given the frequency of unplanned pregnancies, and the long half-life of the drug, inadvertent exposure in pregnancy is likely, even if treatment is discontinued as soon as pregnancy is suspected or confirmed. We therefore propose a pregnancy exposure cohort study to assess the safety of benralizumab use during pregnancy. Information regarding the safety of benralizumab in human pregnancy is essential from a public health perspective to help inform clinical practice.

The Study fulfils a category 3 post-authorisation measure to the The European Medicines Agency's (EMA) Pharmacovigilance Risk Assessment Committee (PRAC).

Research question and objectives: The objectives of the Benralizumab Pregnancy Exposure Study are to monitor planned and unplanned pregnancies exposed to benralizumab and to evaluate the potential teratogenic effect of this medication relative to the primary pregnancy outcome of major structural birth defects and the secondary pregnancy outcomes of preterm delivery, small for gestational age infants, spontaneous abortion, stillbirth, elective termination and postnatal growth to one year of age.

Study design: This is a prospective, observational, exposure cohort study of pregnancy and infant outcomes in women with asthma exposed to benralizumab anytime during pregnancy, or within 8 weeks prior to the first day of the last menstrual period (LMP). The birth prevalence or incidence of outcomes in women exposed to benralizumab, and their infants, will be compared to those observed in two unexposed comparator groups: a disease-matched comparison group of women who have not used benralizumab during pregnancy or within 8 weeks of their last menstrual period (LMP), but who have used other anti-asthmatic medications (treated disease comparison group), and a comparison group of healthy women

who do not have a diagnosis of asthma, have not had exposure to a known human teratogen, and have not taken benralizumab in pregnancy (healthy comparison group).

Population: The study population includes pregnant women who reside in the US or Canada who have or have not used benralizumab anytime in pregnancy for asthma.

Three groups of participants will be enrolled and followed for pregnancy and infant outcomes:

- Pregnant women with asthma exposed to benralizumab anytime during pregnancy or within 8 weeks prior to LMP
- Pregnant women currently treated for asthma not exposed to benralizumab during pregnancy or within 8 weeks prior to LMP
- Pregnant women who are not diagnosed with asthma, have not had exposure to a known human teratogen, and have not taken benralizumab in pregnancy

Variables: Outcome variables include major structural birth defects, spontaneous abortion, stillbirth, elective termination, preterm delivery, infant birth size, postnatal growth of live born children up to one year of age. These will be obtained by maternal report and verified by medical record review. Potential confounders or covariates to be collected include maternal age, race/ethnicity, socioeconomic status, pregnancy and health history, lifestyle factors, comorbidities, medication, vaccine and vitamin/mineral exposures, prenatal tests, and measures of disease severity. Exposure will be defined as benralizumab treatment by maternal report and verified by medical record review, with detailed information on the gestational timing, route of administration, dose, and dates of exposure. Details regarding definitions will be provided in the Statistical Analysis Plan (SAP) to be developed separately and submitted to the agency prior to the submission of the first interim report.

Data sources: Data will be collected using maternal interview(s), medical records (obstetric, delivery hospital, pediatric, allergist and/or other specialty provider), and pregnancy exposure diary. Maternal interview data will be recorded on hard copy forms, and medical record abstraction data will be recorded on electronic forms, and these records will be retained by OTIS. Maternal interview forms are considered the primary data sources for the study. Data from these forms will be extracted and entered into a customized OTIS study database located in the OTIS Research Center and developed specifically for the OTIS studies.

Study size: The target sample size for the study is 200 women in the benralizumab-exposed cohort; 300 women in the treated diseased cohort; and 300 women in the non-diseased cohort.

Statistical method: Demographic and baseline characteristics will be compared between the cohorts. The primary analysis will be a comparison of the prevalence rate of major structural defects in live born infants between the benralizumab-exposed cohort and the treated disease cohort. Where numbers permit, multivariable analyses will be conducted to determine the

relationship of benralizumab with the primary outcome of major structural birth defects, and separately for each of the secondary outcomes of small for gestational age, preterm delivery, spontaneous abortion, stillbirth, elective termination and small for age postnatal growth. There will be no formal hypothesis testing, rather point estimates of the rate ratios along with confidence intervals will be presented.

Milestones: The study is planned for 7 years from start of enrollment (first patient in (FPI) to study completion). There will be 5 years of active recruitment, with an interim report reviewed by the Scientific Advisory Committee each year. The final report with statistical analysis according to the SAP will be prepared at the end of the study.

5. AMENDMENTS AND UPDATES

Table 1 Amendments and updates

Number	Date	Section of study protocol	Amendment or update	Reason
Protocol Version 2.0	03 September 2018	Milestones	Clarify timelines	Response to comments from the EMA
		Sections 4 & 9.5 & 9.7	Revise the sample size justification to reflect the focus is to characterize the degree of uncertainty around estimates, rather than to be used for any formal statistical hypothesis testing, and add 80% CIs to the statistical analyses section. Clarify the focus for analysis of clinical relevance through signal detection, rather than analysing statistical significance	Response to comments from the EMA
		Sections 4, 9.6.1, 9.7.1, 10.1.4, 12.1.2	interim report; annual interim report; interim annual report referenced throughout the protocol are all now referred to as “interim report”	Consistency
		Section 11	Added method of causality assessment of adverse events	Response to comments from the EMA

6. MILESTONES

Table 2 Study milestones

Milestone	Planned date
Start of data collection	September 2018
End of data collection	August 2025
Registration in the EU PAS register	Study not registered
Final report of study results	September 2026

7. RATIONALE AND BACKGROUND

Asthma is a common, life-long inflammatory disease of the airways that affects children and adults of all ages. It is one of the most common long-term diseases worldwide, and can be life threatening. The prevalence of asthma in adults in the United States is estimated at 7% ([National Health Interview Survey, 2001-2003](#)). Prevalence is higher in females than males and has considerably increased in recent years ([National Health Interview Survey, 2001-2003](#)). Symptoms come and go and include shortness of breath, wheezing, chest tightness and cough. The cause of asthma is unknown; however, a family history of asthma, eczema or allergy makes it more likely that an individual will develop asthma.

Although the majority of patients with asthma can be effectively treated with available controller medications, a subset of patients do not adequately respond to current standard therapy. This subset of severe asthma is a heterogenous disease that affects approximately 5-10% of asthmatic patients but is responsible for a disproportionate percentage of the health care costs associated with asthma ([Antonicelli et al., 2004](#); [Godard, 2002](#); [Moore et al., 2007](#)). About thirty percent of severe asthma patients are reported to have severe eosinophilic asthma in which their symptoms are associated with too many eosinophils (≥ 300 cells/mm³) (a type of white blood cells) in the blood and in phlegm in the airways ([R.S.Zeiger, 2018](#)).

Benralizumab is an eosinophil depleting monoclonal antibody (IgG1 kappa). In Europe, it is indicated as an add-on maintenance treatment in adult patients with severe eosinophilic asthma inadequately controlled despite high-dose inhaled corticosteroids plus long-acting β -agonists. Benralizumab is indicated for add-on maintenance treatment of patients with severe asthma, aged 12 years and older in the U.S. and adult patients in Canada, and with an eosinophilic phenotype. It is administered as a 30 mg subcutaneous injection given every 4 weeks for the first 3 doses, followed by 30 mg subcutaneous injection every 8 weeks thereafter. Recently, clinical efficacy of benralizumab 30 mg SC in asthma was confirmed in Phase 3 global safety and efficacy trials in patients on high dose ICS/LABA ([Bleecker et al., 2016](#); [FitzGerald et al., 2016](#); [Nair et al., 2017](#)).

The prevalence of asthma and severe asthma in women of child bearing age, coupled with the chronic nature of treatment and the schedule of doses with which benralizumab is given, makes inadvertent exposure in pregnancy likely. The fact that it is given by injection makes the ascertainment of exposed pregnancies early in gestation and documentation of gestational timing of exposure more feasible than in circumstances where a drug is taken only as needed and not administered by a health care provider. We therefore propose a pregnancy exposure cohort study to assess the safety of benralizumab in pregnancy.

Information regarding the safety of benralizumab in human pregnancy is essential from a public health perspective as inadvertent pregnancy exposure to benralizumab may take place, and safety information for women who may need this medication is necessary to inform clinical practice.

8. RESEARCH QUESTION AND OBJECTIVES

The purpose of the Benralizumab Pregnancy Exposure Study is to evaluate the effect of benralizumab exposure on pregnancy and infant outcomes compared to unexposed diseased and healthy unexposed pregnancies. Below are the study primary and secondary outcomes:

Primary outcome:

- Major structural birth defects

Secondary outcomes:

- Spontaneous abortion/miscarriage
- Stillbirth
- Elective termination/abortion
- Preterm delivery
- Small for gestational age infants
- Small for age postnatal growth of live born children to 1 year of age

9. RESEARCH METHODS

9.1 Study design

This is a prospective, observational, exposure cohort study of pregnancy outcomes in women with asthma exposed to benralizumab anytime during pregnancy or within 8 weeks prior to Last Menstrual Period (LMP) compared to pregnancy outcomes in women with a diagnosis of asthma who are currently treated for asthma but who have not used benralizumab during pregnancy or within 8 weeks prior to LMP but have used other anti-asthmatic medications, (treated disease comparison group), and pregnancy outcomes in women not diagnosed with asthma who have not been exposed to any known teratogens but have potentially been exposed to non-teratogenic agents (non-diseased comparison group).

The study is conducted by the Organization of Teratology Information Specialists (OTIS) Research Center located at the University of California San Diego. The registry relies on voluntary reporting of pregnancy and exposures by women and health care providers who contact the North American OTIS network of teratogen information services as well as other sources of recruitment (see Section 9.2.1 for modalities of recruitment).

The study design is appropriate for the study objectives in that mothers are enrolled before the outcome of pregnancy is known, direct measures of relative and absolute risk can be computed, and a range of adverse pregnancy outcomes can be evaluated. The study design includes the identification of women with benralizumab exposure in pregnancy, and two appropriate comparison groups. Data obtained for the treated diseased group assists with evaluation of the contribution of the underlying maternal disease to adverse pregnancy outcomes, and provides an appropriate comparison group for the benralizumab-exposed cohort. This is essential, in that maternal asthma itself has been associated with a wide variety of adverse pregnancy outcomes (Murphy et al., 2011; J. A. Namazy et al., 2013; Rejno et al., 2014). The non-asthmatic comparison group allows for comparison of asthmatic to non-asthmatic women. If the distribution of underlying disease severity is similar in both the benralizumab and the treated disease group, this could further illuminate the potential contribution of the disease (and disease-severity) to outcomes.

Women who agree to enroll will be consented orally over the telephone, and will then complete the initial telephone interview (See Section 10.1.3 for the consent process). Depending on the gestational timing of enrollment, a number of subsequent telephone interviews will be conducted during pregnancy and after birth. After women sign for release of medical records, medical records for both the woman and infant will be obtained and abstracted for information to validate exposures and outcomes. Enrolled women will be followed until the completion of pregnancy and infants followed up to one year after birth to determine the outcome of pregnancy with respect to primary and secondary study outcomes (refer to Table 7, Section 9.6.2 for more information on the timing of study events)

9.2 Setting

The study population consists of three cohorts of pregnant women (See Section 9.5 for sample size).

Participants will be recruited into the three cohorts concurrently, on the basis of the following inclusion/exclusion criteria:

Cohort 1: Benralizumab-Exposed

Inclusion Criteria:

- Currently pregnant women diagnosed with asthma who contact the OTIS Research Center and who have been exposed to benralizumab for any number of days, at any dose, and at

any time from 8 weeks before the first day of LMP up to and including the end of pregnancy.

- Eligible participants will be currently pregnant women who agree to the conditions and requirements of the study including the interview schedule and release of medical records.

Exclusion Criteria:

- Women who have had exposure to another biologic, used for any indication, anytime during pregnancy or within 8 weeks of LMP.
- Women will not be eligible for Cohort 1 if they first contact the OTIS Research Center after prenatal diagnosis of a major structural birth defect.
- Retrospective cases (outcome of pregnancy known prior to enrollment).
- Women who have enrolled in the current study with a previous pregnancy.

Cohort 2: Treated Diseased Comparison

Inclusion Criteria:

- Currently pregnant women diagnosed with asthma and exposed to asthma medications for any number of days, at any dose, and at any time from LMP up to the date of enrollment, who contact the OTIS Research Center but who were not exposed to benralizumab during pregnancy or within 8 weeks prior to LMP.
- Eligible participants will be currently pregnant women who agree to the conditions and requirements of the study including the interview schedule and release of medical records.

Exclusion Criteria:

- Women with exposure to benralizumab any time during pregnancy or within 8 weeks prior to LMP.
- Women will not be eligible for Cohort 2 if they first come in contact with the OTIS Research Center after prenatal diagnosis of a major structural birth defect.
- Retrospective cases (outcome of pregnancy known prior to enrollment).
- Women who have enrolled in the current study with a previous pregnancy.

Cohort 3: Non-Asthmatic Comparison

Inclusion Criteria:

- Currently pregnant women who contact the OTIS Research Center.
- Eligible women may potentially have been exposed to non-teratogenic agents during this pregnancy.
- Women who agree to the conditions and requirements of the study including the interview schedule and release of medical records.

Exclusion Criteria:

- Women who have been exposed to any known teratogenic agents as determined by the OTIS Research Center (list in Annex 1) for any number of days, at any dose, from the first day of the last menstrual period up to and including the end of pregnancy.
- Women with a self-reported diagnosis of asthma, current or previous.
- Women will not be eligible for Cohort 3 if they come in contact with the OTIS Research Center after prenatal diagnosis of a major structural birth defect.
- Retrospective cases (outcome of pregnancy known prior to enrollment).
- Women who have enrolled in the current study with a previous pregnancy.

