9.5 Study size

The proposed sample sizes in each of the three study groups are as follows:

- 200 women exposed to benralizumab at any time 8 weeks prior to LMP and throughout pregnancy
- 300 women with treated asthma, unexposed to benralizumab, aiming to represent the full spectrum of asthma severity with emphasis on severe patients
- 300 non-asthmatic comparison women

The sample size is considered plausible based on the experience of the OTIS research group with previous studies of asthma in pregnancy, but enrollment rates for the current study are unknown. Although it is unknown to what extent benralizumab will be used by pregnant women, experience with recruitment in the omalizumab (Xolair) EXPECT registry provides some support for the proposed sample size. In six years of recruitment, the EXPECT registry recruited 191 exposed pregnancies ([J. Namazy et al., 2015](#)).

No formal statistical hypothesis testing will be done. Point estimates of the rate ratios and associated CI's between the benralizumab exposed cohort and the unexposed cohorts will be used to evaluate the potential risk of benralizumab to mothers and fetuses.

Table 5 is included to contextualize the magnitude of reported relative risks. This outlines the probability of observing rate ratios in excess of different thresholds either by chance (i.e., when the true underlying risk ratio is 1) or when there is a true underlying increase in risk (RR of 1.2, 1.5 or 2), given the planned sample size.

- If the truth is that there is no increase in risk (true RR=1), the current study would have a relatively small probability (<20%) of reporting out an observed relative risk of 1.5 or greater.
- If the truth is that there is a doubling of risk, the current study would have a higher probability of reporting an observed RR greater than 1.5 ($\geq 70\%$), and a smaller probability of reporting out an observed RR < 1.2 ($\leq 13\%$).

Table 5 Probability that observed relative risk point estimates (exposed/unexposed) will exceed different thresholds

Outcome	Prevalence in unexposed cohort	Expected number of Exposed/ Unexposed Asthmatic cohorts		True RR	Probability observed RR exceeds X			
		enrolled	with complete outcome		X=1.2	X=1.5	X=2.0	X=3.0
All major birth defects in live born infants	3%	200/300	180/270	1	0.38	0.19	0.10	0.02
				1.2	0.51	0.29	0.16	0.04
				1.5	0.68	0.45	0.27	0.08
				2	0.87	0.70	0.49	0.18
Preterm birth	7%	200/300	180/270	1	0.30	0.10	0.02	0.00
				1.2	0.50	0.22	0.06	0.00

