ANNEX 1. LIST OF STAND-ALONE DOCUMENTS

Table 8 List of stand-alone documents

	Document reference number	Date	Title
1	N/A	21 November 2017	Known Human Teratogen

KNOWN HUMAN TERATOGENS – DISQUALIFIERS FOR NON-DISEASED CONTROLS FOR ALL MTB STUDIES:

*For most known teratogens, exposure between LMP and conception is not disqualifying, so consider **post-conception** exposure only. Exceptions: acitretin and etretinate (see notes next to these exposures).*

Exposure	Notes
ACE Inhibitors	Class of medication used to treat high blood pressure
Acitretin	Any exposure within 2 years of LMP.
Alcohol, Heavy	>5 drinks per week or \geq 5 drinks in 1 day: Week = Sun-Sat If MOB gives an estimated range of number of drinks, eligibility is based on the maximum.
Aminopterin	
Antiseizure / Anticonvulsant Medications	
Antineoplastics, Other	Drugs used for the treatment of cancer
Cocaine	
Cytomegalovirus (CMV)	
Type I and Type II Diabetes	Type II Diabetes also listed below
Etretinate	Any exposure within 10 years of LMP.

Fever, High	102 degrees or higher for 24 hours or longer – please ask if fever broke or was consistent
Fluconazole, Systemic	≥7 days total (consecutive or non-consecutive) need to ask if the woman is planning on taking again during pregnancy
Isotretinoin	
Lenalidomide	
Lithium	
Methimazole	
Methotrexate	
Propylthiouracil (PTU)	
Radiation, High Dose	≥ 5 rads to the uterus
Rubella	
Thalidomide	
Toxoplasmosis	
Varicella	Primary case of chicken pox
Warfarin (Coumadin, Jantoven) derivatives	

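### Other biologics are excluded from the benralizumab cohort but not from its primary comparator, with no rationale and little prospect of adjustment; Section 9.2 and Annex 1 also conflict on Cohort 3 eligibility

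*Protocol*

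**What the plan says.** All three points come from the cohort criteria in Protocol Section 9.2 and the list in Annex 1.

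- **Cohort 1 (benralizumab)** excludes "Women who have had exposure to another biologic, used for any indication, anytime during pregnancy or within 8 weeks of LMP".
- **Cohort 2 (treated asthma)** has one drug exclusion: "Women with exposure to benralizumab any time during pregnancy or within 8 weeks prior to LMP". A woman qualifies if she was "exposed to asthma medications for any number of days, at any dose, and at any time from LMP up to the date of enrollment". Another asthma biologic meets that condition. Section 9.5 describes this cohort as "aiming to represent the full spectrum of asthma severity with emphasis on severe patients".
- **Cohort 3 (non-asthmatic)** excludes "Women who have been exposed to any known teratogenic agents as determined by the OTIS Research Center", with a reference to Annex 1. The Annex 1 list is headed "DISQUALIFIERS FOR NON-DISEASED CONTROLS FOR ALL MTB STUDIES" and includes type I and type II diabetes.

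Section 9.7.1 makes Cohort 1 (first-trimester exposed) against Cohort 2 the primary comparison for major structural defects in live births, and adds secondary comparisons with Cohort 3. It allows an adjusted logistic analysis only with at least 30 events in the analysis sample. The sub-analyses in Section 9.7.2 cover effect modifiers, exposure length, timing and dose, prenatal testing, severity and genetic anomalies. None concerns other biologics.

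**The concern.** The protocol treats other biologics as important enough to keep out of the exposed cohort, for every indication, but lets them into the reference group of the primary endpoint. Recruitment of Cohort 2 leans towards severe asthma, which is where another asthma biologic is most likely to be in use. A risk shared across biologics would then sit on both sides of the ratio and shrink it. In a safety study that error runs towards missing a signal.

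The Annex 1 exclusions have the opposite effect in the contrasts with Cohort 3. Women with diabetes or a listed teratogenic exposure can be in Cohorts 1 and 2 but not in the reference, so those ratios can rise above 1 without any effect of benralizumab or asthma.

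Finally, if Section 9.2 and Annex 1 define the Cohort 3 exclusion differently, eligibility depends on which text staff follow.

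**Working it through.** **Inputs from the protocol.** Table 5 gives 180 and 270 evaluable pregnancies in Cohorts 1 and 2 and a 3% defect prevalence in Cohort 2. Section 9.7.1 gives the 30-event rule. The share of Cohort 2 on another biologic (f) and the risk these drugs carry are not in the document. Both are assumed below.

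**1. Table 5.** Exact enumeration of two independent binomials (n = 180 and 270), counting outcomes with observed RR > X, gives for defects P(RR > 1.5) = 0.187 at true RR 1 (Table 5: 0.19) and 0.698 at true RR 2 (Table 5: 0.70). Of the 48 cells, 46 agree within 0.02. The other two (3% prevalence, X = 1.2, true RR 1 and 1.2) agree when ties are counted: 0.377 against 0.38, and 0.508 against 0.51.

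**2. Dilution of the primary RR.** Suppose benralizumab and the other biologics both carry a true RR of 2. The Cohort 2 risk becomes 0.03 × (1 + f), the Cohort 1 risk is 0.06, and the expected RR is 2/(1 + f).

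| f | Expected RR | P(observed RR > 1.5) |
|---|---|---|
| 0% | 2.00 | 0.70 |
| 5% | 1.90 | 0.66 |
| 10% | 1.82 | 0.63 |
| 20% | 1.67 | 0.55 |

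If the other biologics carry no added risk, the expected RR stays at 2.00 for every f.

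**3. Is adjustment available?** Expected defect events in Cohorts 1 and 2:

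- true RR 1: 180 × 0.03 + 270 × 0.03 = 5.4 + 8.1 = 13.5
- true RR 2: 180 × 0.06 + 270 × 0.03 = 10.8 + 8.1 = 18.9

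Adding Cohort 3 (270 evaluable, 3% assumed) gives 21.6 and 27.0. All are below 30.

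**4. Precision cost of the restricted analysis.** At true RR 1 and 3% risk, SE(log RR) = √(1/5.4 − 1/180 + 1/8.1 − 1/270) = 0.547. Removing 10% of Cohort 2 leaves 243 women and 7.29 expected events, and the SE becomes 0.559 (0.559/0.547 = 1.02). Removing 20% leaves 216 women and 6.48 events, and the SE becomes 0.574 (ratio 1.05).

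**5. Contrasts with Cohort 3.** Let a share g of Cohort 1 have an Annex 1 disqualifier with relative risk r, and let benralizumab have no effect. The expected RR is 1 + g(r − 1). With g = 5% it is 1.05, 1.075 and 1.10 for r = 2, 2.5 and 3. With g = 10% and r = 3 it is 1.20. Both g and r are assumed.

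**6. Section 9.2 against Annex 1, for Cohort 3.**

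| | Section 9.2 | Annex 1 |
|---|---|---|
| Start of window | First day of LMP | "For most known teratogens, exposure between LMP and conception is not disqualifying" |
| Amount | Any dose and duration | Thresholds for some, e.g. systemic fluconazole from 7 days, radiation from 5 rads, heavy alcohol, high fever |
| Before LMP | Not covered | Acitretin within 2 years, etretinate within 10 years |

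A woman exposed to a listed drug only between LMP and conception is usually excluded by the first text and admitted by the second. For acitretin or etretinate use that ended before LMP but inside the Annex 1 window, it is the reverse.

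**The case against.** **Cohort 2 is meant to represent other asthma treatment.** On this view the RR compares benralizumab with the alternatives, other asthma biologics included, and is not diluted. That is a legitimate contrast, but it does not explain why biologics for any indication, not only asthma, are barred on one side alone.

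**Sensitivity analyses belong in the SAP.** The SAP is not shown and may contain this restriction. Section 9.3.1 also promises to explore the timing, dose and duration of other asthma medication in the comparison group. This stands as far as a missing analysis goes. The one-sided criterion and its lack of rationale are nonetheless fixed in the protocol.

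**The sizes are assumed.** This stands. At 5% to 10% use, the probability of an observed RR above 1.5 falls only from 0.70 to 0.66–0.63. Section 9.5 reports that a dedicated omalizumab registry took six years to recruit 191 exposed pregnancies, so a large share in Cohort 2 should not be taken for granted.

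**Some secondary outcomes can be adjusted.** Also correct. At Table 5 rates, small for gestational age would give 450 × 0.10 = 45 events and preterm birth 450 × 0.07 = 31.5, above the respective minimums of 30 (logistic) and 20 (Cox). The difficulty is specific to the primary outcome.

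**Cohort 3 is openly defined as healthy and teratogen-free.** True, and diabetes and medications are listed covariates. With about 5 and 8 events, an 80% interval at RR 1 spans a factor of exp(1.28 × 0.547) ≈ 2 either way, so an inflation to 1.08 would not be visible.

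**Amount thresholds may simply define a teratogenic exposure.** That reading is possible, because Section 9.2 defers to the research center's determination. It does not resolve the difference in time windows.

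**Conclusion.** The one-sided biologic exclusion is real, touches the primary comparison and is unexplained. Its effect cannot be sized from the document. Under an assumed shared RR of 2, the expected RR is 1.90, 1.82 and 1.67 at 5%, 10% and 20% use; with no risk from other biologics there is no bias. Adjustment for the primary outcome is not expected to be available.

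A reader might infer more than this:

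- *That exclusions in general are applied to one cohort only.* Three are common to all cohorts: first contact after prenatal diagnosis of a defect, pregnancy outcome already known, and earlier enrolment in the study.
- *That the teratogen and diabetes rule biases the primary result.* Neither Cohort 1 nor Cohort 2 has that exclusion, so the primary comparison is not affected by it. It bears only on secondary contrasts with Cohort 3 and is a minor point.
- *That the primary RR is known to be biased.* The document gives neither the share of other biologics nor their risk.

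The conflict between Section 9.2 and Annex 1 needs no assumption. It is minor, but it decides eligibility.

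**What to change.** 1. In Section 9.7.2, prespecify that the primary RR is reported with and without Cohort 2 women exposed to another biologic in the window used for Cohort 1, and state in Section 9.2 why the exclusion applies to Cohort 1 only. Medication data are already collected. The restricted comparator is smaller (a standard error about 2% to 5% larger at 10% to 20% use) and plausibly loses some of its best matches on severity. Both versions should therefore be shown, and these women should not be barred from enrolment.
2. As a sensitivity analysis, repeat the contrasts with Cohort 3 after restricting Cohorts 1 and 2 to women without an Annex 1 disqualifier. The cost is one further restricted analysis and somewhat fewer women.
3. Reconcile Section 9.2 with Annex 1 on the exposure window, the amounts and the pre-LMP periods for Cohort 3. This is a wording change. Women already enrolled in Cohort 3 should be checked against the agreed rule.
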